4.1.6 Safety Monitoring

- The study will be overseen by an SRC composed of the Medical Monitor and 2 voting members from the Sidney Kimmel Comprehensive Cancer Center at Johns Hopkins. The SRC will convene to review data and discuss next steps at the end of every dose level (once all patients complete the 10-week evaluation period), the data have been cleaned, and the DLT outcomes are determined. In addition, the SRC will meet every 6 months at minimum, and as needed to review AEs. The Principal Investigator and study biostatistician will attend SRC meetings. The SRC will sign off on each dose level before activation of a new dose cohort or expansion of a dose cohort may begin.
- All women of childbearing potential (WOCBP) should be instructed to contact the Investigator immediately if they suspect they might be pregnant (eg, missed or late menstrual period) at any time during study participation. The Investigator must immediately notify the Medical Monitor in the event of a confirmed pregnancy in a patient participating in the study.
- The reason(s) for protocol therapy discontinuation, the reason(s) for study removal, and the corresponding dates must be documented in the Case Report Form (CRF).

- Adverse events will be followed for 30 days after the last dose of LC. Patients removed from the study for unacceptable AEs will be followed until resolution or stabilization of the AE.

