5.1 Inclusion Criteria

Women and members of minority groups will be actively recruited. No exclusion to this study will be based on gender, race, or ethnicity.

Patients are eligible to be included in the study only if all of the following criteria apply:

1. Capable of giving signed informed consent as described in [Section 9.1.3](#) (Appendix 1) that includes compliance with the requirements and restrictions listed in the ICF and in this protocol.
2. ≥ 18 years of age
3. Histologically confirmed HGG (WHO grade III or IV, including GBM, astrocytoma, gliosarcoma, *H3K27M* mutant diffuse midline glioma). Patients with methylated or unmethylated O(6)-methylguanine-DNA methyltransferase (MGMT) promoter are eligible, as are IDH WT and mutant patients as long as the treatment plan is for combined RT/TMZ. The neuropathologic diagnosis of HGG will be made at the respective institution. If any question arises regarding the accuracy of the neuropathologic diagnosis, slides (and pathological blocks, if necessary) will be centrally reviewed.
4. Planning standard therapy with TMZ and RT for 6 weeks
5. Karnofsky Performance Scale (KPS) $\geq 60\%$ ([Section 9.6](#) [Appendix 6])
6. Adequate organ and marrow function defined as:

Hgb	> 9 g/dL
ANC	$\geq 1500/\mu\text{L}$
Platelet count	$\geq 100,000/\mu\text{L}$
Total bilirubin	≤ 1.5 * institutional ULN
AST and ALT	≤ 3 * institutional ULN
Creatinine	≤ 1.5 * institutional ULN

OR

Estimated glomerular filtration rate (eGFR)	≥ 60 mL/min/1.73 m ² unless data exist supporting safe use at lower values of renal function, but eGFR must be ≥ 30 mL/min/1.73 m ²
---	---

7. Patients with human immunodeficiency virus (HIV) who are on effective antiretroviral therapy are eligible if the viral load was assessed as undetectable within 6 months prior to baseline.
8. Women: WOCBP must agree to use adequate contraception (hormonal or barrier method of birth control or abstinence) prior to study entry and for the duration of study participation.

Men: must agree to use adequate contraception prior to study entry, for the duration of study participation, and for 4 months after completion of LC administration.

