7.2.6 Pregnancy

- The effects of LC on the developing human fetus are unknown, but possible teratogenic effects have been observed in animal and in vitro models. For this reason and because LC as well as TMZ used in this trial are known to be

teratogenic, WOCBP and men must agree to use adequate contraception (hormonal or barrier method of birth control; abstinence) prior to study entry and for the duration of study participation. Should a woman become pregnant or suspect she is pregnant while she or her partner is participating in this study, she should inform her treating physician immediately. Men treated or enrolled on this protocol must also agree to use adequate contraception prior to the study, for the duration of study participation, and 4 months after completion of LC administration.

- Pregnant women are excluded from this study because the curcuminoid moiety of LC has the potential for teratogenic or abortifacient effects at high doses. Specifically, mouse studies using high-dose curcumin have suggested lower fetal birth weights ([Chen et al, 2010](#); [Ganiger et al, 2007](#)), and using pegylated curcumin showed reduced live birth rates in mature females ([Murphy et al, 2012](#)). This same study showed hastened onset of puberty in immature female mice, also raising concerns of potential risk for AEs in nursing infants secondary to treatment of the mother with LC, and breastfeeding should therefore be discontinued if the mother is treated with LC. These potential risks may also apply to other agents used in the study, including but not limited to the co-administration with TMZ which is associated with embryo-fetal toxicity.
- Details of all pregnancies in female patients and in female partners of male patients will be collected from the time of consent until 90 days after the last dose of study drug.
- If a pregnancy is reported, the Investigator should inform the Sponsor within 24 hr of learning of the pregnancy and should follow the procedures outlined in [Section 9.5](#) (Appendix 5).
- Abnormal pregnancy outcomes (eg, spontaneous abortion, fetal death, stillbirth, congenital anomalies, ectopic pregnancy) are considered SAEs.

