9.5 Appendix 5: Contraceptive Guidance and Collection of Pregnancy Information

The effects of LC on the developing human fetus are unknown, but possible teratogenic effects have been observed in animal and in vitro models. For this reason and because LC agents as well as other therapeutic agents (TMZ) used in this trial are known to be teratogenic, WOCBP and men must agree to use adequate contraception (hormonal or barrier method of birth control; abstinence) prior to study entry and for the duration of study participation. Should a woman become pregnant or suspect she is pregnant while

she or her partner is participating in this study, she should inform her treating physician immediately. Men treated or enrolled in this study must also agree to use adequate contraception prior to the study, for the duration of study participation, and for 4 months after completion of LC administration.

Pregnant women are excluded from this study because the curcuminoid moiety of LC has the potential for teratogenic or abortifacient effects at high doses. Mouse studies using high-dose curcumin have suggested lower fetal birth weights ([Chen et al, 2010](#); [Ganiger et al, 2007](#)), and pegylated curcumin is associated with reduced live birth rates in mature females (Murphy et al, 2012). The same study showed hastened onset of puberty in immature female mice, raising concerns for AEs in nursing infants of mothers treated with LC. Breastfeeding should be discontinued if a mother is being treated with LC. These potential risks also apply to other agents used in the study, including but not limited to the co-administration of TMZ, which is associated with embryo-fetal toxicity.

Women of Childbearing Potential

A woman is considered fertile following menarche and until becoming postmenopausal unless permanently sterile (see below).

If fertility is unclear (eg, amenorrhea in adolescents or athletes) and a menstrual cycle cannot be confirmed before first dose of study intervention, additional evaluation should be considered.

Women in the following categories are not considered WOCBP:

1. Premenarchal
2. Premenopausal female with 1 of the following:
 - Documented hysterectomy
 - Documented bilateral salpingectomy
 - Documented bilateral oophorectomy

For individuals with permanent infertility due to an alternate medical cause other than the above, (eg, mullerian agenesis, androgen insensitivity), Investigator discretion should be applied to determining study entry.

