Note: Documentation can come from the site personnel's: review of the patient's medical records, medical examination, or medical history interview.

3. Postmenopausal female
 - A postmenopausal state is defined as no menses for 12 months without an alternative medical cause.
 - Females on hormonal replacement therapy (HRT) and whose menopausal status is in doubt will be required to use one of the nonestrogen hormonal highly effective contraception methods if they wish to continue their HRT

during the study. Otherwise, they must discontinue HRT to allow confirmation of postmenopausal status before study enrollment.

Collection of Pregnancy Information

Male patients with partners who become pregnant

- The Investigator will attempt to collect pregnancy information on any male patient's female partner who becomes pregnant while the male patient is in this study. This applies only to male patients who receive study intervention.
- After obtaining the necessary signed informed consent from the pregnant female partner directly, the Investigator will record pregnancy information on the appropriate form and submit it to the Sponsor within 24 hr of learning of the partner's pregnancy. The female partner will also be followed to determine the outcome of the pregnancy. Information on the status of the mother and child will be forwarded to the Sponsor. Generally, the follow-up will be no longer than 6 to 8 weeks following the estimated delivery date. Any termination of the pregnancy will be reported regardless of fetal status (presence or absence of anomalies) or indication for the procedure.

Female Patients who become pregnant

- The Investigator will collect pregnancy information on any female patient who becomes pregnant while participating in this study. Information will be recorded on the appropriate form and submitted to the Sponsor within 24 hr of learning of a patient's pregnancy.
- The patient will be followed to determine the outcome of the pregnancy. The Investigator will collect follow-up information on the patient and the neonate and the information will be forwarded to the Sponsor. Generally, follow-up will not be required for longer than 6 to 8 weeks beyond the estimated delivery date. Any termination of pregnancy will be reported, regardless of fetal status (presence or absence of anomalies) or indication for the procedure.

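### Women's contraception ends with study participation and has no period counted from the last dose, so a woman who withdraws or is lost soon after dosing has no requirement

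*Protocol*

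**What the plan says.** The women's requirement appears in three places. Section 9.5 asks women of childbearing potential to "use adequate contraception (hormonal or barrier method of birth control; abstinence) prior to study entry and for the duration of study participation". Inclusion criterion 8 in Section 5.1 sets the same limits: "hormonal or barrier method of birth control or abstinence) prior to study entry and for the duration of study participation". Section 7.2.6 repeats them.

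In each of these places men have a longer obligation, worded in Section 9.5 as "for the duration of study participation, and for 4 months after completion of LC administration". The reason given for contraception is that LC and TMZ as "used in this trial are known to be teratogenic".

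Three provisions deal with pregnancies that occur:
- Section 7.2.6 has details of pregnancies "collected from the time of consent until 90 days after the last dose of study drug".
- Section 4.1.6 tells women to contact the Investigator "if they suspect they might be pregnant (eg, missed or late menstrual period) at any time during study participation".
- Section 9.5 states: "The Investigator will collect pregnancy information on any female patient who becomes pregnant while participating in this study".

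Section 6.2 lets a patient leave at any time and ends both treatment and study membership at that point. Section 6.3 treats a patient who stays unreachable as withdrawn.

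**The concern.** The women's obligation is tied to membership of the study, not to exposure. If membership ends shortly after a dose, the obligation ends with it. The protocol's own reason for contraception is teratogenicity, and a fetus carried by a treated woman is exposed directly. The protocol does provide a post-dose period for men, and it gives no reason for leaving one out for women.

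What is at stake is a serious and irreversible harm in a small number of patients. No endpoint, dose-limiting toxicity rule or analysis is involved.

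**Working it through.** The protocol states no figure for a post-dose contraception period in women, so there is none to reproduce. The check sets the provisions side by side.

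**Step 1: when each obligation ends.**

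| Provision | Women | Men |
|---|---|---|
| Inclusion criterion 8 (5.1) | End of participation | 4 months after completing LC |
| Section 7.2.6 | End of participation | 4 months after completing LC |
| Section 9.5 | End of participation | 4 months after completing LC |

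**Step 2: when participation ends.**
- *Stops LC but stays in the study.* Sections 6.1 and 4.1.5 continue follow-up, every 2 months for 2 years after the last LC dose and every 6 months after that. On a plain reading she is still participating and still covered.
- *Withdraws fully.* Section 6.2 ends participation at that time.
- *Lost to follow-up.* Section 6.3 counts this as withdrawal, after repeated missed visits and attempts at contact.

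For a patient who withdraws on a dosing day, the required contraception after the last LC dose is therefore 0 days for a woman and 4 months for a man.

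**Step 3: whether another provision fills the gap.**
- The 90 days in Section 7.2.6 are for data collection and do not require contraception.
- The reporting instruction in Section 4.1.6 and the collection rule in Section 9.5 both stop at the end of participation. That is also at odds with the 90 days in Section 7.2.6.
- Section 7.2.2 (related SAEs after discharge) and Section 9.5 (related post-study pregnancy SAEs) apply only to events the Investigator happens to learn of. Section 9.5 says there is no duty to seek them.
- The Schedule of Activities places pregnancy tests before first dosing, at Week 7 and before each adjuvant cycle, with none at End of Treatment.

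None of these sets a contraception requirement after exit.

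**Step 4: scale.** Let t be the days from last dose to exit. The part of the 90-day collection window that falls after exit is 90 − t days, and 0 once t reaches 90.

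| t (days) | Basis | Days left |
|---|---|---|
| 0 | Withdrawal on a dosing day | 90 − 0 = 90 |
| 7 | One nominal weekly LC interval | 90 − 7 = 83 |
| 14 | Assumed: two missed weekly visits | 90 − 14 = 76 |
| 30 | Assumed: slow loss to follow-up or delayed dosing | 90 − 30 = 60 |
| 90 or more | – | 0 |

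These figures show how much of the protocol's own collection window is left without a contraception rule. They are not a clinical shortfall, because the protocol does not state how long women need contraception.

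**The case against.** The strongest points on the other side are these.

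- **The case is narrow.** A woman who remains in survival follow-up is covered for far longer than 4 months. This stands, and the point is limited to full withdrawal and loss to follow-up.
- **Loss to follow-up is slow.** Section 6.3 requires contact attempts first, and a clause cannot be reinforced with someone who cannot be reached. This is fair: the days left shrink as t grows. But the agreement is made at entry, so a period counted from the last dose would still stand after she leaves, as the men's clause already does.
- **Section 6.2 calls, if possible, for an End of Treatment visit.** Counselling could take place there, but the text does not mention contraception.
- **The consent form may cover it.** Inclusion criterion 1 requires "compliance with the requirements and restrictions listed in the ICF and in this protocol". The consent form is not shown, so what patients are told cannot be judged. This limits the point to the protocol text.
- **Persistence is short and the need is not quantified.** The protocol gives a TMZ half-life of 1.8 hr and mean residence times of 0.18–0.62 hr for curcumin. It also calls TMZ potentially mutagenic, so some post-dose period may well be right. Its length cannot be derived from this document, and the men's 4 months do not set it for women.
- **The 90 days are a data window, so they should not serve as a floor.** As a clinical requirement they are indeed unproven. As a minimum for internal consistency they are reasonable, because the sponsor already regards pregnancies up to that point as worth collecting.

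**Conclusion.** The concern holds. Followed as written, the protocol sets no contraception requirement for a woman who fully withdraws, or is counted as withdrawn, soon after a dose. The required period after exit is 0 days. With withdrawal on a dosing day, the whole 90-day pregnancy-collection window falls outside any requirement; one nominal week later, 83 days do.

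The conclusion rests on two readings: that participation includes survival follow-up, and that it ends on withdrawal or loss to follow-up. The protocol gives no withdrawal rate and no sex or age mix. The number of women affected is therefore not estimated; with at most 30 treated patients of both sexes it is likely small. The change should be made because the possible harm is serious and the correction is cheap.

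**What to change.** In inclusion criterion 8, Section 7.2.6 and Section 9.5, require women of childbearing potential to use contraception throughout participation and for a defined period after the last dose of LC or TMZ, whichever is later. State that this also applies after withdrawal or loss to follow-up. The sponsor's clinical team should set the length, at no less than the 90 days already used for pregnancy collection in Section 7.2.6.

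Replace the participation limit in the Section 4.1.6 reporting instruction and in the Section 9.5 collection rule for female patients with the 90 days after the last dose from Section 7.2.6.

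The cost is one clause in three sections and one phrase in each of two. The only burden is a defined post-treatment contraception period for a few women. No endpoint, dose-limiting toxicity rule, sample size or analysis changes.

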9.6 Appendix 6: Karnofsky Performance Scale

Table 20. Karnofsky Performance Scale

Percent	Description
100	Normal, no complaints, no evidence of disease
90	Able to carry on normal activity; minor signs or symptoms of disease
80	Normal activity with effort; some signs or symptoms of disease
70	Cares for self; unable to carry on normal activity or to do active work
60	Requires occasional assistance, but is able to care for most of his/her needs
50	Requires considerable assistance and frequent medical care
40	Disabled, requires special care and assistance
30	Severely disabled, hospitalization indicated. Death not imminent
20	Very sick, hospitalization indicated. Death not imminent
10	Moribund, fatal processes progressing rapidly
0	Dead

